7.8.1 Primary Efficacy Endpoint(s)

The primary efficacy endpoint is SBM frequency at Week 1; an SBM is defined as any BM that does not occur within 24 hours after rescue medication use. Since rescue medication use will be disallowed during Week 1, the SBM frequency should equal the BM frequency. In the case of protocol violators, the analysis will be based on SBMs.

In order to adjust for early withdrawals or those with less than 7 days diary data, weekly SBM frequency will be calculated as follows:

$$7 \times (\text{Number of SBMs} / \text{Number of days}),$$

where the number of days is the number of days during the week that the subject was in the study. Weeks will be calculated as 168-hour intervals starting from the day after randomization (Day1), if there is no time recorded for the morning dose on Day1 then the time of the first recorded morning dose will be used. The number of days will generally be 7 unless a subject drops out during a treatment week. If the number of days is less than 4, then the data will be considered insufficient and the frequency will be missing.

Primary Analysis

Since outliers are commonly observed in these data, parametric models may not be robust. The efficacy data will therefore be analyzed by a van Elteren test stratified by center. If necessary, small centers will be pooled as mentioned above. This procedure will test the null hypothesis of equal SBM rates between treatments at the end of Week 1 versus the alternative hypothesis of non-equality between the 2 groups; the test will be conducted at a 2-sided significance level of 0.05. A related 95% confidence interval and point estimate will be provided for the treatment difference; the confidence interval will be estimated by inverting the hypothesis test. This endpoint will be analyzed for the FAS.

Sensitivity Analyses

The primary analysis as described above will be repeated using the PP rather than the FAS. An additional sensitivity analysis using the FAS assuming a ‘worse-case’ scenario approach will also be conducted, where missing values, including those with < 4 days diary data, are assigned the worst case values (the lowest SBM frequency for week 1) recorded in the study by any subject for that endpoint at that time.

Additionally the endpoint will be analyzed using robust analysis of variance (ANOVA) models (by M-estimation [3] using PROC ROBUSTREG in SAS) with center and treatment in the model as a sensitivity analysis using the FAS. The interaction between treatment and center will also be examined in a separate model, using robust ANOVA methods as previously described.

To examine the effects of any permanent dose reduction in response to an AE (as recorded on the eCRF) an additional sensitivity analysis will also be performed. This will be performed on the FAS where data from those subjects with a dose reduction will be excluded from the time of dose reduction (taken as date of last BID dose + 12 hours, e.g. if the evening dose is removed

CROSS-REGIONAL TEMPLATE

Template Number: C-TMPL-DO-801

Page: 19 of 28

Version Number: 1.2

Effective Date: 14 Sep 2015

This version replaces: 1.1

Parent Document: C-SOP-DO-800

Template Title: Statistical Analysis Plan (Legacy Takeda)

then the time will be from the morning dose + 12 hours, if the morning dose is removed then it will be from the previous day's evening dose + 12 hours) and subjects will be treated as a drop-out from this time point onwards. This will be implemented using robust ANOVA. Additionally, another factor will be added to the robust ANOVA model to examine the effect of dose reduction. This will be performed on the FAS. This analysis will not be carried out if the number of subjects with a dose reduction within the first week is less than 5%.

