7.0 METHODS OF ANALYSIS AND PRESENTATION

7.1 GENERAL PRINCIPLES [OR CONSIDERATIONS]

Continuous data will be summarized using number of subjects (N), mean, standard deviation (SD), median, minimum, and maximum. Summary statistics for continuous data will only include subjects with a non-missing value for the data being summarized.

Categorical data will be summarized using the number and percent of subjects for each category where appropriate. Missing categories will be used for categorical data when missing data is present. The calculation of percentages will take into account missing responses.

All confidence intervals, statistical tests, and resulting p-values will be reported as 2-sided unless otherwise stated. P-values (when rounded to three decimals) less than or equal to α ($=0.05$) are reported as “statistically significant”.

Means, LS means, and medians will be presented to 1 more decimal place than the recorded data. Where presented, SDs and standard errors will be presented to 2 more decimal places than the recorded data. Confidence intervals for parameter estimates will be presented using the same number of decimal places as those recorded for the parameter point estimate.

Alternative methods of analysis of the data may be considered prior to un-blinding should some of the assumptions underlying the proposed analyses not be met. However, the reasons for any departures from the planned approach and methods will be documented fully.

Centers may be pooled geographically if necessary for analysis purposes.

Version 9.4 or later of SAS®, will be used to provide all data summaries, statistical analyses, and data listings.

CROSS-REGIONAL TEMPLATE

Template Number: C-TMPL-DO-801

Page: 10 of 28

Version Number: 1.2

Effective Date: 14 Sep 2015

This version replaces: 1.1

Parent Document: C-SOP-DO-800

Template Title: Statistical Analysis Plan (Legacy Takeda)

Study Visit Windows

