7.8 EFFICACY ANALYSIS

The primary and secondary endpoints will be derived from the daily diary data entered by patients.

Two-sided tests at a significance level of $\alpha=5\%$ will be used throughout unless otherwise stated. The null hypothesis is that lubiprostone is equal to placebo against the alternative that lubiprostone is different to placebo. All analyses will be performed using the FAS. Analyses specified for the PP are to be regarded as supportive evidence. There will be no adjustment for multiplicity.

All efficacy endpoints will be summarized by treatment and visit. If baseline measures are also defined and collected for an efficacy endpoint then change from Baseline at each visit will also be presented by summary statistics by treatment and visit. Change from baseline will be calculated as (post-baseline value) – (baseline value). Baseline is defined as the last recorded measurement prior to treatment.

For diary data, baseline values will be the average of all diary data from the screening period (Days -14 through -1, inclusive, relative to day of first dose). If more than 14 days of diary data are collected during the screening period only the data from Day -14 onwards will be used. If fewer than 8 days are available then the baseline value will be set to missing.

Centers may be pooled geographically if necessary for analysis purposes. This will be determined before database lock.

CROSS-REGIONAL TEMPLATE

Template Number: C-TMPL-DO-801

Page: 17 of 28

Version Number: 1.2

Effective Date: 14 Sep 2015

This version replaces: 1.1

Parent Document: C-SOP-DO-800

Template Title: Statistical Analysis Plan (Legacy Takeda)

For weekly SBM frequency, at least 4 days of diary data are required to compute a weekly estimate, if there are less than 4 days recorded in a week then the SBM frequency for that week will be set to missing.

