As the primary endpoint is within the first week of study treatment and only 4 days of diary collection are required it is not anticipated that missing values should be a cause of concern therefore the LOCF technique will be used to impute missing values for efficacy analysis purposes only. For a given subject, the most recent nonmissing data point will be carried forward to the subsequent week where data are missing. Details for each efficacy parameter are given below. It is expected, based on previous studies, that the number of subjects with in-sufficient post baseline data for the primary endpoint will be small therefore a simple approach to handling missing data will be used. Where there is no post baseline efficacy data then the baseline value will be used, it is expected that the number of SBMs should increase for those on treatment, therefore using a baseline value for missing post baseline data assumes no treatment effect, this approach can be considered conservative,. To examine the effect of the requirement to have at least a minimum of 4 days post baseline efficacy data for the primary endpoint an additional analysis, stratified by center, of the primary endpoint, using the stratified van Elteren test [2], will be conducted using all valid SBM data post baseline even when less than 4 days data is present, only where there is no post baseline data will baseline be used in this analysis.

An SBM is defined as any BM that does not occur within 24 hours after rescue medication use. Certain periods after taking rescue medication will be defined as “blackout periods” during which BMs are considered as non-spontaneous. Blackout periods, including those with missing or partial times for rescue medication use in the diary, will be handled as follows:

0-24 hours post rescue medication intake if the time is fully specified.

0-24 hours post rescue medication intake if the hour is present, but the minute is missing. The blackout time will commence from the imputed time. If the minutes are incomplete or missing from either the rescue medication or bowel movement entry then it is assumed that the missing values are zero and an imputed time will be calculated. e.g.

1	5			=	1	5	0	0
2	1	5		=	2	1	5	0

0-48 hours, beginning from midnight on the day the rescue medication intake is recorded for, if the hour is missing from the time entry for the rescue medication.

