Box plots will be produced for each weekly measure (SBM frequency, mean degree of straining, mean degree of stool consistency and weekly abdominal symptoms scores) by treatment over time from baseline to Week 4. Additionally graphs presenting histograms of SBM frequency will also be produced by treatment for each week.

CROSS-REGIONAL TEMPLATE

Template Number:	C-TMPL-DO-801	Page:	18 of 28
Version Number:	1.2	Effective Date:	14 Sep 2015
This version replaces:	1.1		
Parent Document:	C-SOP-DO-800		
Template Title:	Statistical Analysis Plan (Legacy Takeda)		

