7.8.2 Secondary Efficacy Endpoint(s)

The interaction of treatment and center and the effect of dose reduction will not be examined for any secondary endpoints. All secondary endpoints will be analyzed for the FAS only.

SBM frequency at Week 2, 3 and 4

The secondary endpoint will be analyzed as specified for the primary endpoint separately for each week.

Additionally for patients with a missing Week 2 frequency estimate (where diary days < 4 in Week 2) the Week 1 estimate will be carried forward, if available. For the worse-case analysis all missing Week 2 values will be assigned the lowest SBM frequency for week 2.

Proportion of subjects with an SBM within 24 hours after first dose

The 24 hour period will be taken from the time of the first recorded dose in the patient diary. If the efficacy data is missing for the first 24 hours following this dose then it will be assumed that the patient did not experience any BM (including SBMs) during this period, this is based on the assumption that a patient is more likely to complete the diary on any particular day if they experience a BM than if they did not. The proportion of subjects with an SBM within 24 hours after first dose in Week 1 will be analyzed by a Cochran-Mantel-Haenszel (CMH) test stratified by center. Additionally a logistic regression model will be used with treatment and center as factors as a sensitivity analysis. The estimated odds ratio and associated 95% CI for both methods will be presented to aid interpretation of the clinical effect.

Mean Degree of Straining (Week 1, 2, 3, and 4)

For each BM patients should indicate the degree of straining associated with that BM. The degree of straining is a 5 point scale:

0 = No straining

1 = Mild straining

2 = Moderate straining

3 = Strong straining

4 = Very strong straining

CROSS-REGIONAL TEMPLATE

Template Number: C-TMPL-DO-801

Page: 20 of 28

Version Number: 1.2

Effective Date: 14 Sep 2015

This version replaces: 1.1

Parent Document: C-SOP-DO-800

Template Title: Statistical Analysis Plan (Legacy Takeda)

For each subject, the mean degree of straining will be averaged for all SBMs in a given week. The mean degree of straining will then be analyzed by van Elteren tests, stratified by center, at Weeks 1, 2, 3, and 4 separately. A related 95% confidence interval and point estimate will be provided for the treatment difference; the confidence interval will be estimated by inverting the hypothesis test.

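### Optional improvement: the supportive robust ANOVA for SBM frequency omits the baseline that the SAP already derives, so no baseline-adjusted difference with an interval is pre-specified

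*SAP*

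**What the plan says.** **Primary test.** SAP 7.8.1: "The efficacy data will therefore be analyzed by a van Elteren test stratified by center". A point estimate and a 95% CI come from inverting that test. Baseline is not used.

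**Supportive model.** SAP 7.8.1 adds a robust ANOVA by M-estimation, "with center and treatment in the model as a sensitivity analysis using the FAS". The variants are a treatment-by-center interaction and a dose-reduction factor. The ordinary ANOVA in protocol 13.1.3.1 also has only center and treatment. For SBM frequency at Weeks 2 to 4, SAP 7.8.2 states: "The secondary endpoint will be analyzed as specified for the primary endpoint separately for each week".

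**Baseline.** SAP 7.8 averages the diary over Days -14 to -1 and adds a rule: "If fewer than 8 days are available then the baseline value will be set to missing". The baseline then has three uses:
- Descriptive change scores: "change from Baseline at each visit will also be presented by summary statistics by treatment and visit". SAP 7.1 sets the content of such summaries: "Continuous data will be summarized using number of subjects (N), mean, standard deviation (SD), median, minimum, and maximum".
- Box plots of the weekly measures "by treatment over time from baseline to Week 4".
- Imputation: "Where there is no post baseline efficacy data then the baseline value will be used".

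None of these is a covariate adjustment. ANCOVA is in the SAP's abbreviation list, but no readable method uses it. Redacted analyses cannot be checked.

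**The concern.** If the arms differ by chance in baseline SBM frequency, a reader of the results will ask how much of the Week 1 difference depends on that. The summaries and box plots would show the gap. They would not give an adjusted difference with an interval. An adjusted model added after the gap has been seen would be post hoc.

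The change scores answer only in part. They are summarized without an interval for the treatment difference, and subtracting baseline fixes its slope at 1 whatever the data show.

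Such gaps do occur in this programme. Protocol Table 4.a gives baseline means in SC0232 of 1.52 (placebo) and 1.28 (lubiprostone), p=0.012. The other two trials in the table show no imbalance (p=0.612 and p=0.873).

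**Working it through.** **Inputs**
- SAP 6.0: difference 5.9 - 4 = 1.9, SD 4, two-sided alpha 0.05, power 90%, total 198, raised to 204 (102 per arm).
- Protocol Table 4.a: group sizes and SDs at baseline and Week 1.
- Correlation between baseline and Week 1 (rho): not in the documents. Assumed 0.1, 0.2 and 0.3. Low values are more plausible because protocol 7.1 caps entry below 3 SBM per week, which narrows the baseline range.

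**1. The plan's own figure.** Noncentral t power, with n multiplied by the Wilcoxon efficiency 3/pi, is 89.8% at 98 per arm and 90.1% at 99 per arm. So 99 per arm, 198 in total, is the smallest size that reaches 90%. The 198 reproduces and does not rely on baseline adjustment.

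**2. Precision.** Adjustment changes the residual SD to 4 x sqrt(1 - rho^2). With the same formula at 99 per arm:

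| rho | Residual SD | CI width, relative | Power |
|---|---|---|---|
| no covariate | 4.00 | 100% | 90.1% |
| 0.1 | 3.98 | 99.5% | 90.4% |
| 0.2 | 3.92 | 98.0% | 91.2% |
| 0.3 | 3.82 | 95.4% | 92.6% |

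A normal approximation with an assumed M-estimation efficiency of 0.95 gives nearly the same range, 90.3% to 92.7%. If baseline carries no information, the cost is one degree of freedom. In a simulation with 102 per arm, 10 centers, skewed counts and 600 replicates, the mean SE then rose from 0.507 to 0.509.

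**3. Effect of a one-SE baseline gap.** The SE of the gap is SD_base x sqrt(2/102), and the slope is rho x SD_week1 / SD_base. The shift in the unadjusted difference is the product, rho x SD_week1 x sqrt(2/102), so SD_base cancels. Here sqrt(2/102) = 0.140. The SDs from Table 4.a are pooled within arm.

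| Source | Week 1 SD | Shift at rho 0.1 | Shift at rho 0.3 |
|---|---|---|---|
| SC0131 | 3.54 | 0.05 | 0.15 |
| SC0232 | 3.43 | 0.05 | 0.14 |
| SC0831 | 2.35 | 0.03 | 0.10 |
| Planning SD | 4 | 0.06 | 0.17 |

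The planning-SD row is 3% to 9% of the planned 1.9.

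**4. How often a gap like SC0232's would occur.** That gap is 1.52 - 1.28 = 0.24. The table gives the probability of 0.24 or more in either direction at 102 per arm.

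| Baseline SD from | SD | SE of gap | Probability |
|---|---|---|---|
| SC0131 | 1.32 | 0.185 | 19% |
| SC0232 | 0.84 | 0.118 | 4% |
| SC0831 | 0.77 | 0.109 | 3% |

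Where the gap is commoner it matters less. At rho 0.1 to 0.3, a 0.24 gap shifts the difference by 0.06 to 0.19 with SC0131's SDs and by 0.10 to 0.29 with SC0232's.

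**5. When change scores are exact.** Their slope of 1 is right when rho = SD_base / SD_week1. That is 1.32/3.54 = 0.37 (SC0131), 0.84/3.43 = 0.25 (SC0232) and 0.77/2.35 = 0.33 (SC0831). Pairing SC0232's baseline SD with the planning SD gives 0.84/4 = 0.21. With SC0232's SDs, a 0.24 gap leaves (slope - 1) x 0.24 = -0.14, -0.04 and +0.05 in the change-score difference at rho 0.1, 0.2 and 0.3.

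**The case against.** The strongest reply is that nothing needs repair. Randomization already allows for chance imbalance, so the center-stratified test holds its level without baseline, and it comes with an estimate and a 95% CI. The two-term model follows the protocol. The change-score summaries give N, mean and SD by arm, from which an interval could be calculated, and protocol 13.1 provides for a blinded review of whether the planned methods are appropriate. Every size shown above rests on an assumed correlation. All of this stands, and it is why the point is optional.

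The reply does not remove the gap. An interval calculated by a reader from change scores is not a pre-specified adjusted result, and it still forces the slope to 1.

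Some cost also stands. The added fits fall in a plan without multiplicity adjustment, so they must be labelled supportive. For a subject whose outcome is imputed from baseline, the outcome equals the covariate, which is a reason to allow a repeat fit without those subjects.

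A reader might infer that the change scores mislead unless the correlation is close to 0.21. Table 4.a does not support that: 0.21 mixes one trial's baseline SD with the planning SD, and the trials' own SDs give 0.25 to 0.37.

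**Conclusion.** The point holds as an optional, low-cost improvement to a supportive analysis. No readable SBM-frequency analysis yields a pre-specified baseline-adjusted treatment difference with an interval, although the SAP already derives the baseline. At assumed correlations of 0.1 to 0.3, power rises by 0.3 to 2.5 points. A one-SE gap moves the unadjusted difference by 0.03 to 0.17 SBM per week, depending on the SD used. The main benefit is a ready answer if the arms turn out unbalanced; the gain in precision is secondary.

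Two stronger readings are not supported. One is that the primary analysis is invalid or the trial undersized without baseline; the test is valid under randomization and the 198 reproduces without adjustment. The other is that SC0232 shows the conclusion to be at risk; its baseline gap ran against lubiprostone, and Week 1 was still significant at P<0.001.

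**What to change.** Keep the van Elteren test and the two-term robust ANOVA. Before unblinding, add to SAP 7.8.1:

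> The robust ANOVA (M-estimation) will also be fitted with treatment, center and baseline weekly SBM frequency (FAS), beside the current two-term model. The estimated treatment difference and its 95% CI will be reported from both models. For the covariate only, a baseline missing under the 8-day rule is set to the overall mean of both arms; this value is not used to impute an outcome. The same model is used for Weeks 2, 3 and 4. The adjusted fit is supportive and does not alter the primary conclusion.

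The sentence on the difference and its CI is needed because SAP 7.8.1 names no estimate or interval for the robust model. A repeat fit without subjects whose outcome was imputed from baseline may be added; it would examine that imputation.

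**Cost.** Four supportive fits (one per week) and one missing-covariate rule. There are no new data and no change to the primary test, alpha or sample size. SAP 7.13 already says that the SAP contains analyses beyond the protocol.

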7.8.2 Secondary Efficacy Endpoint(s)

The interaction of treatment and center and the effect of dose reduction will not be examined for any secondary endpoints. All secondary endpoints will be analyzed for the FAS only.

SBM frequency at Week 2, 3 and 4

The secondary endpoint will be analyzed as specified for the primary endpoint separately for each week.

Additionally for patients with a missing Week 2 frequency estimate (where diary days < 4 in Week 2) the Week 1 estimate will be carried forward, if available. For the worse-case analysis all missing Week 2 values will be assigned the lowest SBM frequency for week 2.

Proportion of subjects with an SBM within 24 hours after first dose

The 24 hour period will be taken from the time of the first recorded dose in the patient diary. If the efficacy data is missing for the first 24 hours following this dose then it will be assumed that the patient did not experience any BM (including SBMs) during this period, this is based on the assumption that a patient is more likely to complete the diary on any particular day if they experience a BM than if they did not. The proportion of subjects with an SBM within 24 hours after first dose in Week 1 will be analyzed by a Cochran-Mantel-Haenszel (CMH) test stratified by center. Additionally a logistic regression model will be used with treatment and center as factors as a sensitivity analysis. The estimated odds ratio and associated 95% CI for both methods will be presented to aid interpretation of the clinical effect.

Mean Degree of Straining (Week 1, 2, 3, and 4)

For each BM patients should indicate the degree of straining associated with that BM. The degree of straining is a 5 point scale:

0 = No straining

1 = Mild straining

2 = Moderate straining

3 = Strong straining

4 = Very strong straining

CROSS-REGIONAL TEMPLATE

Template Number: C-TMPL-DO-801

Page: 20 of 28

Version Number: 1.2

Effective Date: 14 Sep 2015

This version replaces: 1.1

Parent Document: C-SOP-DO-800

Template Title: Statistical Analysis Plan (Legacy Takeda)

For each subject, the mean degree of straining will be averaged for all SBMs in a given week. The mean degree of straining will then be analyzed by van Elteren tests, stratified by center, at Weeks 1, 2, 3, and 4 separately. A related 95% confidence interval and point estimate will be provided for the treatment difference; the confidence interval will be estimated by inverting the hypothesis test.

Additionally the endpoint will be analyzed using robust analysis of variance (ANOVA) models with center and treatment in the model as a sensitivity analysis.

If there are no SBMs during the week or if there are SBMs but all ratings are missing, then the LOCF method will impute the average from the average used for the most recent week. For Week 1 analysis where there is no value to carry forward then a value of 4 will be assumed. This assumption will be carried into later weeks if LOCF does not provide an estimate.

Mean Degree of Stool Consistency (Week 1, 2, 3, and 4)

For each BM patients should indicate the type of stool consistency associated with that BM. The degree of stool consistency is assessed using the Bristol Stool Scale [3]; a 7 point scale, where decreasing values indicate harder stools:

Type 1		Separate hard lumps, like nuts (hard to pass)
Type 2		Sausage-shaped but lumpy
Type 3		Like a sausage but with cracks on its surface
Type 4		Like a sausage or snake, smooth and soft
Type 5		Soft blobs with clear-cut edges (passed easily)
Type 6		Fluffy pieces with ragged edges, a mushy stool
Type 7		Watery, no solid pieces, entirely liquid

Stool consistency will be analyzed in the same manner described for the degree of straining. For Week 1 analysis, where there is no value to carry forward, then a value of 1 will be assumed. This assumption will be carried into later weeks if LOCF does not provide an estimate.

CROSS-REGIONAL TEMPLATE

Template Number: C-TMPL-DO-801 **Page:** 21 of 28
Version Number: 1.2 **Effective Date:** 14 Sep 2015
This version replaces: 1.1
Parent Document: C-SOP-DO-800
Template Title: Statistical Analysis Plan (Legacy Takeda)

Weekly Abdominal Symptoms Score (Bloating and Discomfort) (Week 1, 2, 3, and 4)

The abdominal symptom score should be completed by patients in their diary, every 7 days on the last day of each treatment week upon waking in the morning. Patients should indicate the degree of abdominal bloating and discomfort experienced over the past week.

Abdominal Bloating	0 = None: No abdominal distension 1 = Mild: Slight abdominal distension 2 = Moderate: Abdominal distension clearly felt 3 = Severe: Severe abdominal distension 4 = Very severe: Extremely strong abdominal distension
Abdominal Discomfort	0 = None: No abdominal discomfort 1 = Mild: Slight abdominal discomfort 2 = Moderate: Abdominal discomfort clearly felt 3 = Severe: Abdominal discomfort with pain 4 = Very severe: Abdominal discomfort with severe pain

The abdominal symptoms (bloating and discomfort) will be analyzed separately by van Elteren tests, stratified by center, at Weeks 1, 2, 3, and 4. A related 95% confidence interval and point estimate will be provided for the treatment difference; the confidence interval will be estimated by inverting the hypothesis test.

Additionally a cumulative logistic regression model will be used with treatment and center as factors as a sensitivity analysis. The estimated odds ratio and associated 95% CI will also be presented to aid interpretation of the clinical effect. The interaction between treatment and center will also be examined in a separate model.

If the assessment ratings are missing, then the LOCF method will impute the value from the value used for the most recent week. For Week 1 analysis where there is no value to carry forward then a value of 4 will be assumed. This assumption will be carried into later weeks if LOCF does not provide an estimate.

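### For straining and stool consistency, SAP 7.8.2 scores an observed week without an SBM by the same rule as blank ratings, so its score depends on whether an earlier treatment week was rated

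*SAP*

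**What the plan says.** SAP 7.8.2 averages the straining rating over all SBMs in a week and tests each of Weeks 1 to 4 separately with a stratified van Elteren test. The average is undefined when the week has no SBM. The rule for that case is: "If there are no SBMs during the week or if there are SBMs but all ratings are missing, then the LOCF method will impute". What gets carried is the previous score; the SAP says it will "impute the average from the average used for the most recent week", and that earlier value may itself have been imputed.

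For the first week: "For Week 1 analysis where there is no value to carry forward then a value of 4 will be assumed". Four is the top of the 0-4 straining scale. If nothing becomes available later, "This assumption will be carried into later weeks if LOCF does not provide an estimate".

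Consistency follows suit: "Stool consistency will be analyzed in the same manner described for the degree of straining". Its first-week value differs: "For Week 1 analysis, where there is no value to carry forward, then a value of 1 will be assumed". Type 1 is the hardest stool on the seven-point Bristol scale.

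Three other places bear on this:
- SAP 7.8 has a general fallback for efficacy data: "Where there is no post baseline efficacy data then the baseline value will be used".
- Protocol 13.1.3 limits LOCF to treatment-period data. It plans supportive analyses without imputation and with worst recorded values.
- SAP 7.7 describes daily diary questions on whether there was a bowel movement and whether rescue medication was used.

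**The concern.** A week with a completed diary and no SBM is known information. For SBM frequency, SAP 7.8 and 7.8.1 count such a week as an observed zero, provided at least 4 diary days exist. For straining and consistency, the same week is handled as if the subject had forgotten to fill in a rating.

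This has two consequences. First, the same event can receive very different scores, depending only on whether an earlier treatment week had a rated SBM. Second, every Week 1 subject without an SBM is placed at the extreme of the scale. If the arms differ in how many such subjects they have, that difference in frequency appears as a difference in straining or consistency, even if the drug changes neither. Protocol 6.2 adds these endpoints so that they supplement frequency, so overlap with the primary endpoint weakens their purpose. A subject who had Week 1 SBMs but left the ratings blank is also scored at the extreme, with no evidence of a bad outcome.

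**Working it through.** The plan gives no figure on this point, and the sample size does not depend on it. The check has three parts.

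**1. The rule applied to example subjects**

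| Subject | Observed | Straining score |
|---|---|---|
| A | Week 1 mean 1.0; no SBM in Week 2 | Week 2 = 1.0 (carried) |
| B | No SBM in Week 1 | Week 1 = 4 |
| C | No SBM in Weeks 1 and 2 | 4 in both weeks |
| D | SBMs in Week 1, all ratings blank | Week 1 = 4 |

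A's Week 2 and B's Week 1 are the same event, scored 4 − 1.0 = 3 points apart on a 0-4 scale. For consistency, a Week 1 mean of 4.0 followed by no SBM is scored 4.0, while no SBM in Week 1 is scored 1, again 3 points apart.

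**2. How often Week 1 has no SBM**

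The documents give no such rate. As an assumption, a negative binomial was fitted to each Week 1 mean m and SD s in Protocol Table 4.a:

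k = m² / (s² − m), P(0) = (k / (k + m))^k

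For placebo in SC0131, m = 3.46 and s = 2.28, so s² = 5.198, k = 11.972 / 1.738 = 6.89 and P(0) = (6.89 / 10.35)^6.89 = 0.061.

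| Study | Placebo | Lubiprostone | Subjects expected per 102 |
|---|---|---|---|
| SC0131 | 6.1% | 5.5% | 6.2 vs 5.7 |
| SC0232 | 5.5% | 3.3% | 5.6 vs 3.4 |
| SC0831 | 6.4% | 1.2% | 6.5 vs 1.2 |

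**3. Effect on the Week 1 straining test when the drug does not change straining**

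Assumptions not in the documents: straining mean 1.8 and SD 0.9 in both arms among subjects with an SBM. There were 102 subjects per arm, no-SBM subjects were scored 4, and an unstratified two-sided Wilcoxon test at 5% stood in for van Elteren. The expected false difference (placebo minus lubiprostone) is (4 − 1.8) × (difference in no-SBM rates).

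| No-SBM rates | False mean difference | Rejection rate |
|---|---|---|
| SC0131 | 2.2 × 0.005 = 0.01 | about 5% |
| SC0232 | 2.2 × 0.0215 = 0.05 | 5-6% |
| SC0831 | 2.2 × 0.052 = 0.11 | 9-10% |
| 10% vs 3% (hypothetical) | 2.2 × 0.07 = 0.15 | about 14% |
| 15% vs 5% (hypothetical) | 2.2 × 0.10 = 0.22 | about 23% |

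The rejection rate stays at about 5% in every row if only subjects with an SBM are analysed.

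**The case against.** Several points on the other side are sound.

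- **Worst rank is not obviously the cure.** Scoring every no-SBM week as worst would extend the mixing with frequency to Weeks 2-4. A separate Week 2 simulation assumed mean 1.8, SD 0.8 and correlation 0.6 between weeks. With no true difference and no-SBM rates of 10% vs 5%, rejection was 4% under LOCF and 10% under worst score. With a true difference of 0.3 and equal 10% rates, power was 74% under LOCF and 57% under worst score. Choosing between a composite and a score conditional on having an SBM is an estimand decision, and the documents do not settle it.
- **The protocol already plans an analysis without imputation**, which would remove both the carry-forward and the fixed scores. SAP 7.13 says the SAP adds detail and does not withdraw protocol analyses. This stands in part. For these two endpoints the SAP lists only robust ANOVA as a sensitivity analysis, and it spells out the worst-case analysis only for SBM frequency.
- **The SAP may add detail.** Protocol 13.1 leaves variable definitions to the SAP, so naming a Week 1 value is not in itself a departure.

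A reader might also infer three stronger things that the documents do not support:

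- *That scoring flips with the week number.* It flips with the existence of an earlier rated week. Subject C keeps 4 throughout, and a poor earlier score is carried forward as poor.
- *That carry-forward conceals relapse.* SBM frequency is tested separately in Weeks 2, 3 and 4 and plotted weekly, so relapse is visible there. No SBM is also not the same as no bowel movement, because movements within 24 hours after rescue are excluded.
- *That SAP 7.8 squarely contradicts 7.8.2.* The baseline sentence is justified by SBM counts, and the same paragraph defers to details for each parameter below it. The endpoint-specific text is the natural controlling rule. Only a statement of precedence is missing.

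**Conclusion.** The point holds. SAP 7.8.2 merges an observed outcome with missing data, so identical no-SBM weeks can be scored 3 points apart, and blank Week 1 ratings are scored as the worst result. The diary can tell the two events apart.

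The size is modest. At the rates implied by the two US studies, Week 1 false rejection is about 5% and 5-6%, which is close to nominal. At the Japanese study's rates it is 9-10%. The 14% and 23% figures rest on rates found nowhere in the documents and should not be read as expected. All the rejection figures depend on the assumed straining distribution, the negative binomial form and an unstratified test. The consistency test follows the same rule but was not simulated. Type 1 is worst only in the sense of hardest, since types 6 and 7 are loose or watery.

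The primary endpoint and sample size are unaffected. With no multiplicity adjustment, each weekly secondary test is read at 5%, so the wording is worth correcting before unblinding.

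**What to change.** In SAP 7.8.2, for straining and stool consistency:

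1. Derive a flag from existing diary fields that separates weeks with no SBM from weeks with SBMs but all ratings blank.
2. For blank ratings, assign no fixed 4 or 1. Carry forward a treatment-period value if one exists; otherwise leave the score missing, as Protocol 13.1.3 implies.
3. Pre-specify one rule for no-SBM weeks and apply it identically in Weeks 1 to 4. If worst rank is chosen, label all four weekly tests as composites of frequency and symptom, and define worst for the Bristol scale.
4. Carry the protocol's analysis without imputation into the SAP for both endpoints, and report the number of no-SBM subjects by arm and week beside each result.
5. State that the endpoint-specific rule takes precedence over the general baseline fallback in SAP 7.8.

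The cost is a few sentences and a little programming, with no new data collection. Scores in some weeks may become less favourable, or be missing, for a few subjects.
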